11.4.1 Epacadostat

Dose reductions/Interruptions - Epacadostat

In some circumstances, it may be necessary to temporarily interrupt both study treatments as a result of AEs that may have an unclear relationship to study drug. If an interruption is necessary both study treatments should be interrupted.

Any interruptions of> 2 weeks or for LFT abnormalities must be discussed with the medical monitor before resuming treatment. Treatment with both study drugs should be withheld for drug-related Grade 4 hematologic toxicities, nonhematological toxicity Grade 3 (including laboratory abnormalities), and severe or life-threatening AEs.

Epacadostat may be dose reduced according to the guidelines and dose levels described in Table 14.

Dosing interruptions may be permitted in the case of medical/surgical events or logistical reasons not related to study therapy (eg, elective surgery, unrelated medical events,

subject vacation, and/or holidays). Subjects will be placed back on study therapy within 3 weeks of the scheduled interruption. The reason for interruption should be documented in the subject's study record.

For patients who do not tolerate the RP2D of epacadostat in combination with pembrolizumab, three dose reductions are permitted (Table 14) in order to allow the patient to continue on study drug. The following guidelines need to be applied and these changes must be recorded on the Dosage Administration Record. Please refer to Table 15 for dose reduction steps and criteria for interruption and re-initiation of epacadostat for drug-related toxicities. Doses held during the study will not be made up. When toxicity that resulted in a dose reduction improves to grade 1 or less, the dose can be re-escalated at the investigators discretion provided there are no other concomitant toxicities.

Table 14 Dose Modification Algorithm for Adverse Events Associated with Epacadostat

Epacadostat Dose Levels	Dose Level 1 (starting dose)	Dose Level -1	Dose Level -2
Actual Dose	100mg bid	50mg bid	25mg bid

Table 15. Dose Modification Guidelines for Epacadostat Related Adverse Effects without Immune Etiology

Toxicity	Grade	Hold	Timing for	Dose for	Discontinue
		Treatment	Treatment	Treatment	Subject (after
		(Y/N)	Restart	Restart	discussion with PI)
Hematologic	1,2,3	No	N/A	N/A	N/A
Toxicity					
	4	Yes	Permanently discontinue treatment	N/A	Permanently discontinue study treatment
Non Hematologic Toxicity	1	No	N/A	N/A	N/A

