Immune-related AEs	Toxicity Grade or Conditions (CTCAEv4.0)	Study Medication	Action Taken with Study Medication	irAE Management with Corticosteroid and/or Other Therapies	Monitor and Follow-up
		Pembrolizuma b	Withhold until Grade 0- 1	Administer corticosteroid s (prednisone l-2mg/kg or	Monitor changes of renal function
			Withhold until Grade 0-1	equivalent) followed by taper.	
Nephritis and Renal Dysfunction	Grade 2	Epacadostat	Related: Reduce by 1 dose level.		
			Not Related: Same dose level.		
	Grade 3 or 4	Pembrolizuma b	Permanent! y discontinue		
		Epacadostat	Permanent! y discontinue		
		Pembrolizmnab	Continue	 Manage with topical steroids with 	
Rash	1 or 2	Epacadostat	Continue	or without drug interruption.	
	3 c	Pembrolizumab	Withhold until Grade 0-1	• Administer corticosteroids (initial dose of 1-2 mg/kg prednisone or equivalent) followed by taper.	• If toxicity does not resolve within 12 weeks of last dose, or cannot taper below 10 mg or less of
		Epacadostat	Withhold until Grade 0-1		prednisone or equivalent within 12 weeks, must permanently discontinue.

Immune-related AEs	Toxicity Grade or Conditions (CTCAEv4.0)	Study Medication	Action Taken with Study Medication	irAE Management with Corticosteroid and/or Other Therapies	Monitor and Follow-up
			Related: Reduce by 1 dose level. Not Related: Same dose level.		• Restart epacadostat at same dose if rash is mild and assessed as Grade 3 based only on body surface area and resolves without oral steroids. If oral steroids are required, or rash is severe, decrease by 1 dose level once resolved to Grade 0-1.
		Pembrolizumab	Permanently discontinue	Administer corticosteroids (initial dose of	
	4	Epacadostat	Permanently discontinue	1-2 mg/kg prednisone or equivalent) followed by taper.	
	3	Pembrolizumab	May continue treatment with medical monitor approval		Pennanently discontinue if clinical signs and symptoms of pancreatitis
Asymptomatic d Amylase or Lipase Increased		Epacadostat	May continue treatment with medical monitor approval		develop (abdominal pam, nausea, vomiting). • If toxicity does
	4	Pembrolizumab	Withhold until toxicity resolves to Grade 0-1e		not resolve within 12 weeks of last dose after an
		Epacadostat	Withhold until toxicity resolves to Grade 0-1e Related: Reduce by		interruption, must pennanently discontinue unless approved by the medical monitor to continue.

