- 3. Participants with Grade 3 rash in the absence of desquamation, no mucosa] involvement, does not require systemic steroids, and resolves to Grade 1 within 14 days does not have to hold study medication
- 4. If Grade 4 lipase/amylase elevation is asymptomatic and abdominal imaging suggests no pathology, study drug administration dosing may continue (with or without dose reduction) with medical monitor approval.

Abbreviations: AEs = adverse events; ALT (SGPT) = alanine aminotransferase (serum glutamic pyruvic transaminase); AST (SGOT) = aspartate aminotransferase (serum glutamic oxaloacetic transaminase); CTCAE = Common Terminology Criteria for Adverse Events; OKA= diabetic ketoacidosis; IV = intravenous; irAE = infusion-related adverse events; TlDM = Type 1 diabetes mellitus

*For patients with liver metastases who begin treatment with Grade 2 AST or ALT, if AST or ALT levels remain grade 2 after study treatment the combination of pembrolizumab/epacadostat may continue at the same dose level without any need to withhold treatment. If AST/ALT resolve to grade 0/1 at any time point following initiation of study treatment and then subsequently increase to grade 2 the guidelines recommended in the section of this table entitled "AST / ALT Elevation or Increased Bilirubin" should be followed.

Procedures for Other Immune-Mediated Adverse Reactions, Including Ocular Manifestations

Epacadostat should be permanently discontinued for severe (Grade 4) irAEs. Systemic corticosteroids treatment should be initiated at a dose of 1 to 2 mg/kg per day of prednisone or equivalent for severe irAEs.

Corticosteroid eye drops should be administered to subjects who develop uveitis, iritis, or episcleritis. Epacadostat should be permanently discontinued for immune-mediated ocular disease that is unresponsive to local immunosuppressive therapy.

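### For grade 3 rash, Table 16 sets the epacadostat restart dose by two rules that can disagree, and its no-hold exception turns on an outcome unknown when the hold is decided

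*Combined protocol and SAP*

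**What the plan says.** All the main instructions are in protocol section 11.4.1, in Table 16 and its notes.

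- **Hold.** The grade 3 rash row withholds both drugs until the rash is back to grade 0-1. The row carries a marker c. Note 3 then says that a grade 3 rash without desquamation or mucosal involvement that "does not require systemic steroids, and resolves to Grade 1 within 14 days does not have to hold study medication".
- **Restart dose, Action column.** "Related: Reduce by 1 dose level. Not Related: Same dose level".
- **Restart dose, Follow-up column.** Epacadostat resumes at the "same dose if rash is mild and assessed as Grade 3 based only on body surface area and resolves without oral steroids". Otherwise: "If oral steroids are required, or rash is severe, decrease by 1 dose level once resolved to Grade 0-1".
- **Steroids.** The management cell of the row reads "Administer corticosteroids (initial dose of 1-2 mg/kg prednisone or equivalent) followed by taper", with no condition attached.
- **General text.** Earlier in section 11.4.1: "Treatment with both study drugs should be withheld for drug-related Grade 4 hematologic toxicities, nonhematological toxicity Grade 3". That sentence makes no exception for rash.
- **Appendix B, A2.9.** For grade 3 rash, pembrolizumab is held with no exception, and oral steroids are recommended from 1 mg/kg.

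**The concern.** Two adjacent cells of one row use different criteria for the same decision, and nothing says which prevails. Two sites, or one site on two occasions, could give similar patients different epacadostat doses and both be within protocol.

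Note 3 raises a separate problem of timing. Whether to hold must be decided when the rash is graded, but one condition of the exception is how the rash turns out over the following two weeks.

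Rash was the most frequent grade 3 treatment-related event in the phase 1 study of this combination (text with Table 9), so the row is likely to be used. At stake are patient safety, consistent dosing of both drugs, and the meaning of the interruption and reduction rates that the trial will report.

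**Working it through.** The plan states no design figure on this point. The check is a comparison of texts plus a small amount of arithmetic.

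**1. Restart dose.** Cross the Action column's criterion with the two situations named in the Follow-up column:

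| Grade 3 rash | Action column | Follow-up column | Agree? |
|---|---|---|---|
| Related; mild, body surface area only, no oral steroids | one level lower | same dose | No |
| Related; oral steroids needed, or severe | one level lower | one level lower | Yes |
| Not related; mild, body surface area only, no oral steroids | same dose | same dose | Yes |
| Not related; oral steroids needed, or severe | same dose | one level lower | No |

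Two of the four combinations conflict.

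**2. Timing of note 3.** Epacadostat is taken twice daily without a break (sections 4.2 and 9.1). Doses due before the 14-day condition is settled: 14 days × 2 = up to 28. This is a ceiling, because a need for systemic steroids, desquamation or mucosal involvement would end the exception sooner. Pembrolizumab is given every 21 days (±3 days). A rash starting on cycle day 8 reaches its 14-day limit on day 8 + 14 = 22, which is the next infusion day. With a later onset, an infusion can fall due before the outcome is known.

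**3. Steroids.** The management cell, read alone, gives systemic steroids to every grade 3 rash. The same-dose restart and note 3 both presuppose some grade 3 rashes managed without them. The row does not say which rashes those are.

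**4. How often the row applies.** Inputs: 5 subjects with grade 3 or higher related rash at 100 mg twice daily (section 11.2.1); 117 subjects at that dose (Table 10); 30 patients planned (section 14.1).

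- Rate: 5/117 = 0.043, which reproduces the protocol's 4.3%.
- Expected number: 30 × 0.043 = 1.3 patients.
- Chance of at least one: 1 − (1 − 0.043)^30 = 0.73.

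These figures count every grade 3 or higher related rash. The documents do not show how many would fall in the two conflicting combinations.

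**The case against.** Much can be said for the table, and several stronger readings fail.

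- **Hold.** A reader might infer that the row and note 3 simply contradict each other. The documents do not support that. The markers a to d in the table match notes 1 to 4 in order and subject, so marker c plausibly points to note 3. The note is also permissive. This is a rule with a flagged exception. What remains is that the exception rests on a later outcome and is missing from the general hold text.
- **Steroids.** A reader might infer that a site cannot comply with all the instructions. But the text introducing Table 16 calls the supportive measures suggested, and the Follow-up cell provides for courses with and without oral steroids. This is an ambiguity and not an impossibility.
- **Appendix B.** A2.9 has no exception, which might look like a competing rule. Section 11.4.2 makes Table 16 the reference for withholding pembrolizumab, and Appendix B describes its measures as suggested. The two texts should be aligned, but A2.9 does not override the table.
- **Restart dose.** The relatedness wording recurs across many rows, so the rash-specific Follow-up cell could be read as the governing one. Section 11.4.1 also allows re-escalation at the investigator's discretion once the toxicity is grade 1 or less. Both points soften the conflict. Neither states a precedence or tells the site which dose to restart.
- **Frequency.** Table 9 gives 5/62 (8%), which would imply 30 × 5/62 = 2.4 patients and a 92% chance of at least one. That table pools 25 to 300 mg twice daily, with 20 of the 62 subjects at 300 mg. Section 3.0 reports more grade 3 rash at 300 mg than at 100 mg. The 100 mg figure is the applicable one.

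**Conclusion.** The concern holds in two respects, with a lesser ambiguity beside them. The grade 3 rash row contains two restart-dose rules that disagree in two of four combinations, with no stated precedence. The no-hold exception depends on an outcome up to 14 days away and is not carried into the general hold text of section 11.4.1. The condition under which the steroid instruction applies is also unclear.

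The size is modest: about 1.3 of 30 patients with any grade 3 or higher related rash, and about a 73% chance of at least one. This assumes that the 100 mg rate from the earlier study carries over to this population and that patients are independent. That rate comes from short follow-up (mean exposure 62.0 days in the 99 phase 2 subjects), so it could be low for longer treatment. The number actually meeting conflicting instructions would be some unknown part of these patients.

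A reader might infer that the response result is compromised. The documents do not show that: the 10% and 30% response rates, the 6-of-30 rule and the error rates in section 14.1 do not depend on this row. It is a wording inconsistency that should be corrected for safety and consistent dosing.

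**What to change.** The sponsor should reconcile the grade 3 rash row of Table 16 (Action, steroid and Follow-up cells), note 3, the general hold text in section 11.4.1 and Appendix B A2.9, so that:

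1. one criterion, or a stated order of precedence, sets the epacadostat restart dose;
2. the hold exception is worded so that it can be applied when the decision is made, and is cross-referenced wherever the hold is stated;
3. it is clear for which grade 3 rashes the steroid instruction applies.

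The content of each rule, including what becomes of the 14-day condition, is for the sponsor's clinical team. The cost is an amendment rewording one table row, one note, one sentence and one appendix paragraph, with no added procedures.

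Section 16.3 refers to the study as completed. If no patient remains on treatment, the useful step is to report, for each grade 3 rash, whether treatment was held, whether systemic steroids were given, and which restart-dose rule was used.

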11.4.2 Pembrolizumab

Dose reductions - Pembrolizumab

Dose reductions of pembrolizumab are not permitted.

Dose Modification (Escalation/Titration/Other)

Adverse events (both non-serious and serious) associated with pembrolizumab exposure may represent an immunologic etiology. These adverse events may occur shortly after the first dose or several months after the last dose of treatment. Pembrolizumab must be withheld for drug-related toxicities and severe or life-threatening AEs as per table 16 above.

Other allowed dose interruption for pembrolizumab

Dosing interruptions are permitted in the case of medical / surgical events or logistical reasons not related to study therapy (e.g., elective surgery, unrelated medical events, patient vacation, and/or holidays). Subjects should be placed back on study therapy within 3 weeks of the scheduled interruption, unless otherwise discussed with the Sponsor. The reason for interruption should be documented in the patient's study record.

11.5 Guidelines for the management of specific and immune-related toxicities

Subjects should receive appropriate supportive care measures for immune-related toxicities related to pembrolizumab as deemed necessary by the treating investigator (see Appendix B).

Management of Infusion Reactions: Signs and symptoms usually develop during or shortly after drug infusion and generally resolve completely within 24 hours of completion of infusion.

Table 17 below shows treatment guidelines for subjects who experience an infusion reaction associated with administration of pembrolizumab (MK-3475).

Table 17 Infusion Reaction Treatment Guidelines

NCI CTCAE Grade	Treatment	Premedication at subsequent dosing
Grade 1 Mild reaction; infusion interruption not indicated; intervention not indicated	Increase monitoring of vital signs as medically indicated until the subject is deemed medically stable in the opinion of the investigator.	None
Grade 2 Requires infusion interruption but responds promptly to symptomatic treatment (e.g., antihistamines, NSAIDS, narcotics, IV fluids);	Stop Infusion and monitor symptoms. Additional appropriate medical therapy may include but is not limited to: IV fluids Antihistamines	Subject may be premedicated 1.5h (± 30 minutes) prior to infusion of pembrolizumab (MK-3475) with:

Approval date: 07-May-2024

r dosing prophylactic medications indicated for< = 24 hrs NSAIDS Acetaminophen Narcotics Increase monitoring of vital signs as medically indicated until the subject is deemed medically stable in the opinion of the investigator. If symptoms resolve within one hour of stopping drug infusion, the infusion may be restarted at 50% of the original infusion rate (e.g., from 100 mUhr to 50 ml/hr). Otherwise dosing will be held until symptoms resolve and the subject should be premedicated for the next scheduled dose. Subjects who develop Grade 2 toxicity despite adequate premedication should be permanently discontinued from further trial treatment administration. Grade 3: Prolonged (i.e., not rapidly responsive to symptomatic medication and/or brief interruption of infusion); recurrence of symptoms following initial improvement; hospitalization indicated for other clinical sequelae (e.g., renal impairment, pulmonary infiltrates) Grade 4: Life-threatening; pressor or ventilatory support indicated Increase monitoring of vital signs as medically indicated until the subject is deemed medically stable in the opinion of the investigator. Hospitalization may be indicated. Subject is permanently discontinued from further trial treatment administration. Appropriate resuscitation equipment should be available in the room and a physician readily available during the period	NCI CTCAE Grade	Treatment	Premedication at subsequent	
Acetaminophen Narcotics Increase monitoring of vital signs as medically indicated until the subject is deemed medically stable in the opinion of the investigator. If symptoms resolve within one hour of stopping drug infusion, the infusion may be restarted at 50% of the original infusion rate (e.g., from 100 mUhr to 50 m/hr). Otherwise dosing will be held until symptoms resolve and the subject should be premaently discontinued from further trial treatment administration. Grades 3 or 4 Grade 3: Prolonged (i.e., not rapidly responsive to symptomatic medication and/or brief interruption of infusion); recurrence of symptoms following initial improvement; hospitalization indicated for other clinical sequelae (e.g., renal impairment, pulmonary infiltrates) Grade 4: Life-threatening; pressor or ventilatory support indicated Life-threatening; pressor or ventilatory support indicated Life-threatening; pressor or ventilatory support indicated Subject is permanently discontinued from further trial treatment administration. Acetaminophen Narcotics Acetaminophen of interapy may include but is not limited to: IV fluids Antihistamines No subsequent dosing Increase monitoring of vital signs as medically indicated until the subject is deemed medically stable in the opinion of the investigator. Hospitalization may be indicated. Subject is permanently discontinued from further trial treatment administration.	prophylactic modications indicated	·	•	
Narcotics Increase monitoring of vital signs as medically indicated until the subject is deemed medically stable in the opinion of the investigator. If symptoms resolve within one hour of stopping drug influsion, the influsion may be restarted at 50% of the original influsion rate (e.g., from 100 mUhr to 50 ml/hr). Otherwise dosing will be held until symptoms resolve and the subject should be premedicated for the next scheduled dose. Subjects who develop Grade 2 toxicity despite adequate premedication should be permanently discontinued from further trial treatment administration. Grade 3: Prolonged (i.e., not rapidly responsive to symptomatic medication and/or brief interruption of influsion); recurrence of symptoms following initial improvement; hospitalization indicated for other clinical sequelae (e.g., renal impairment, pulmonary infiltrates) Grade 4: Life-threatening; pressor or ventilatory support indicated Subject is permanently discontinued from further trial treatment administration. Actiminate of vital signs as medically indicated until the subject is deemed medically stable in the opinion of the investigator. Hospitalization may be indicated. Subject is permanently discontinued from further trial treatment administration.				
Increase monitoring of vital signs as medically indicated until the subject is deemed medically stable in the opinion of the investigator. If symptoms resolve within one hour of stopping drug infusion, the infusion may be restarted at 50% of the original infusion rate (e.g., from 100 mUhr to 50 ml/hr). Otherwise dosing will be held until symptoms resolve and the subject should be premedicated for the next scheduled dose. Subjects who develop Grade 2 toxicity despite adequate premedication should be permanently discontinued from further trial treatment administration. Grade 3: Prolonged (i.e., not rapidly responsive to symptomatic medication and/or brief interruption of infusion); recurrence of symptoms following initial improvement; hospitalization indicated for other clinical sequelae (e.g., renal impairment, pulmonary infiltrates) Grade 4: Life-threatening; pressor or ventilatory support indicated Increase monitoring of vital signs as medically stable in the opinion of the investigator. Hospitalization may be indicated. Subject is permanently discontinued from further trial treatment administration.	101 - 241110	•	'	
medically indicated until the subject is deemed medically stable in the opinion of the investigator. If symptoms resolve within one hour of stopping drug infusion, the infusion may be restarted at 50% of the original infusion rate (e.g., from 100 mUhr to 50 ml/hr). Otherwise dosing will be held until symptoms resolve and the subject should be premedicated for the next scheduled dose. Subjects who develop Grade 2 toxicity despite adequate premedication should be permanently discontinued from further trial treatment administration. Stop Infusion. Additional appropriate medical therapy may include but is not limited to: IV fluids Antihistamines NSAIDS Acetaminophen 500-1000 mg po (or equivalent dose of antipyretic). Acetaminophen 500-1000 mg po (or equivalent dose of antipyretic). Acetaminophen 500-1000 mg po (or equivalent dose of antipyretic).			antimotariino).	
deemed medically stable in the opinion of the investigator. If symptoms resolve within one hour of stopping drug infusion, the infusion may be restarted at 50% of the original infusion rate (e.g., from 100 mlbr to 50 ml/hr). Otherwise dosing will be held until symptoms resolve and the subject should be premedicated for the next scheduled dose. Subjects who develop Grade 2 toxicity despite adequate premedication should be permanently discontinued from further trial treatment administration. Stop Infusion. Additional appropriate medical therapy may include but is not limited to: IV fluids Pressors indicated for other clinical sequelae (e.g., renal impairment, pulmonary infiltrates) Grade 4: Life-threatening; pressor or ventiliatory support indicated Increase monitoring of vital signs as medically indicated until the subject is deemed medically stable in the opinion of the investigator. Hospitalization may be indicated. Subject is permanently discontinued from further trial treatment administration.		3 3	Acetaminophen 500-1000 mg	
investigator. If symptoms resolve within one hour of stopping drug infusion, the infusion may be restarted at 50% of the original infusion rate (e.g., from 100 mUhr to 50 ml/hr). Otherwise dosing will be held until symptoms resolve and the subject should be premedicated for the next scheduled dose. Subjects who develop Grade 2 toxicity despite adequate premedication should be permanently discontinued from further trial treatment administration. Stop Infusion. Additional appropriate medical therapy may include but is not limited to: IV fluids Antihistamines NSAIDS Acetaminophen Narcotics Oxygen Pressors Corticosteroids Epinephrine Increase monitoring of vital signs as medically indicated until the subject is deemed medically stable in the opinion of the investigator. Hospitalization may be indicated. Subject is permanently discontinued from further trial treatment administration.		,		
If symptoms resolve within one hour of stopping drug infusion, the infusion may be restarted at 50% of the original infusion rate (e.g., from 100 mUhr to 50 ml/hr). Otherwise dosing will be held until symptoms resolve and the subject should be premedicated for the next scheduled dose. Subjects who develop Grade 2 toxicity despite adequate premedication should be permanently discontinued from further trial treatment administration. Stop Infusion. Stop Infusion. Additional appropriate medical therapy may include but is not limited to: IV fluids Antihistamines NSAIDS Acetaminophen Narcotics Oxygen Pressors Corticosteroids Epinephrine Increase monitoring of vital signs as medically stable in the opinion of the investigator. Hospitalization may be indicated. Subject is permanently discontinued from further trial treatment administration.			. , .	
stopping drug infusion, the infusion may be restarted at 50% of the original infusion rate (e.g., from 100 mUhr to 50 ml/hr). Otherwise dosing will be held until symptoms resolve and the subject should be premedicated for the next scheduled dose. Subjects who develop Grade 2 toxicity despite adequate premedication should be permanently discontinued from further trial treatment administration. Grades 3 or 4 Grade 3: Prolonged (i.e., not rapidly responsive to symptomatic medication and/or brief interruption of infusion); recurrence of symptoms following initial improvement; hospitalization indicated for other clinical sequelae (e.g., renal impairment, pulmonary infiltrates) Grade 4: Life-threatening; pressor or ventilatory support indicated Increase monitoring of vital signs as medically indicated until the subject is deemed medically stable in the opinion of the investigator. Hospitalization may be indicated. Subject is permanently discontinued from further trial treatment administration.		9	anapyreae).	
restarted at 50% of the original infusion rate (e.g., from 100 mUhr to 50 ml/hr). Otherwise dosing will be held until symptoms resolve and the subject should be premedicated for the next scheduled dose. Subjects who develop Grade 2 toxicity despite adequate premedication should be permanently discontinued from further trial treatment administration. Grade 3: Grade 3: Frolonged (i.e., not rapidly responsive to symptomatic medication and/or brief interruption of infusion); recurrence of symptoms following initial improvement; hospitalization indicated for other clinical sequelae (e.g., renal impairment, pulmonary infiltrates) Grade 4: Life-threatening; pressor or ventilatory support indicated Increase monitoring of vital signs as medically indicated until the subject is deemed medically stable in the opinion of the investigator. Hospitalization may be indicated. Subject is permanently discontinued from further trial treatment administration.		* *		
(e.g., from 100 mUhr to 50 ml/hr). Otherwise dosing will be held until symptoms resolve and the subject should be permedicated for the next scheduled dose. Subjects who develop Grade 2 toxicity despite adequate premedication should be permanently discontinued from further trial treatment administration. Grade 3: Prolonged (i.e., not rapidly responsive to symptomatic medication and/or brief interruption of infusion); recurrence of symptoms following initial improvement; hospitalization indicated for other clinical sequelae (e.g., renal impairment, pulmonary infiltrates) Grade 4: Life-threatening; pressor or ventilatory support indicated (e.g., remal impairment, pulmonary infiltrates) Grade 4: Life-threatening; pressor or ventilatory support indicated (e.g., remal impairment, pulmonary infiltrates) Increase monitoring of vital signs as medically indicated until the subject is deemed medically stable in the opinion of the investigator. Hospitalization may be indicated. Subject is permanently discontinued from further trial treatment administration.				
Otherwise dosing will be held until symptoms resolve and the subject should be premedicated for the next scheduled dose. Subjects who develop Grade 2 toxicity despite adequate premedication should be permanently discontinued from further trial treatment administration. Grades 3 or 4 Grade 3: Prolonged (i.e., not rapidly responsive to symptomatic medication and/or brief interruption of infusion); recurrence of symptoms following initial improvement; hospitalization indicated for other clinical sequelae (e.g., renal impairment, pulmonary infiltrates) Grade 4: Life-threatening; pressor or ventillatory support indicated Increase monitoring of vital signs as medically indicated until the subject is deemed medically stable in the opinion of the investigator. Hospitalization may be indicated. Subject is permanently discontinued from further trial treatment administration.		3		
resolve and the subject should be premedicated for the next scheduled dose. Subjects who develop Grade 2 toxicity despite adequate premedication should be permanently discontinued from further trial treatment administration. Grades 3 or 4 Stop Infusion. Additional appropriate medical therapy may include but is not limited to: IV fluids Antihistamines NSAIDS Acetaminophen Narcotics Oxygen indicated for the next scheduled dose. Subjects who develop Grade 2 toxicity despite adequate from further trial treatment administration. No subsequent dosing No subsequent dosing No subsequent dosing No subsequent dosing Additional appropriate medical therapy may include but is not limited to: IV fluids Antihistamines NSAIDS Acetaminophen Narcotics Oxygen Pressors Corticosteroids Epinephrine Increase monitoring of vital signs as medically indicated until the subject is deemed medically stable in the opinion of the investigator. Hospitalization may be indicated. Subject is permanently discontinued from further trial treatment administration.		,		
premedicated for the next scheduled dose. Subjects who develop Grade 2 toxicity despite adequate premedication should be permanently discontinued from further trial treatment administration. Stop Infusion. Additional appropriate medical therapy may include but is not limited to: IV fluids Antihistamines NSAIDS Acetaminophen Narcotics Oxygen Pressors Corticosteroids Epinephrine Increase monitoring of vital signs as medically indicated. Subject is permanently discontinued from further trial treatment administration.		•		
Subjects who develop Grade 2 toxicity despite adequate premedication should be permanently discontinued from further trial treatment administration. Grades 3 or 4 Grade 3: Prolonged (i.e., not rapidly responsive to symptomatic medication and/or brief interruption of infusion); recurrence of symptoms following initial improvement; hospitalization indicated for other clinical sequelae (e.g., renal impairment, pulmonary infiltrates) Grade 4: Life-threatening; pressor or ventilatory support indicated Increase monitoring of vital signs as medically stable in the opinion of the investigator. Hospitalization may be indicated. Subject is permanently discontinued from further trial treatment administration.				
despite adequate premedication should be permanently discontinued from further trial treatment administration. Stop Infusion. Stop Infusion. Additional appropriate medical therapy may include but is not limited to: IV fluids Antihistamines NSAIDS Acetaminophen Narcotics Oxygen Pressors (e.g., renal impairment, pulmonary infiltrates) Grade 4: Life-threatening; pressor or ventilatory support indicated despite adequate premedication should be permanently discontinued from further trial treatment administration. No subsequent dosing		•		
Stop Infusion.				
Trial treatment administration. Grades 3 or 4 Stop Infusion.		·		
Grades 3 or 4 Grade 3: Prolonged (i.e., not rapidly responsive to symptomatic medication and/or brief interruption of infusion); recurrence of symptoment; hospitalization indicated for other clinical sequelae (e.g., renal impairment, pulmonary infiltrates) Grade 4: Life-threatening; pressor or ventilatory support indicated Grade 4: Life-threatening; pressor or ventilatory support indicated Stop Infusion. Additional appropriate medical therapy may include but is not limited to: IV fluids Antihistamines NSAIDS Acetaminophen Narcotics Oxygen Pressors Corticosteroids Epinephrine Increase monitoring of vital signs as medically indicated until the subject is deemed medically stable in the opinion of the investigator. Hospitalization may be indicated. Subject is permanently discontinued from further trial treatment administration.		•		
Grade 3: Prolonged (i.e., not rapidly responsive to symptomatic medication and/or brief interruption of infusion); recurrence of symptoms following initial improvement; hospitalization indicated for other clinical sequelae (e.g., renal impairment, pulmonary infiltrates) Grade 4: Life-threatening; pressor or ventilatory support indicated Additional appropriate medical therapy may include but is not limited to: IV fluids Antihistamines NSAIDS Acetaminophen Narcotics Oxygen Pressors Corticosteroids Epinephrine Increase monitoring of vital signs as medically indicated until the subject is deemed medically stable in the opinion of the investigator. Hospitalization may be indicated. Subject is permanently discontinued from further trial treatment administration.	Overden Overd		N	
Grade 3: Prolonged (i.e., not rapidly responsive to symptomatic medication and/or brief interruption of infusion); recurrence of symptoms following initial improvement; hospitalization indicated for other clinical sequelae (e.g., renal impairment, pulmonary infiltrates) Grade 4: Life-threatening; pressor or ventilatory support indicated Increase monitoring of vital signs as medically indicated until the subject is deemed medically stable in the opinion of the investigator. Hospitalization may be indicated. Subject is permanently discontinued from further trial treatment administration.	Grades 3 or 4	•	No subsequent dosing	
Prolonged (i.e., not rapidly responsive to symptomatic medication and/or brief interruption of infusion); recurrence of symptoms following initial improvement; hospitalization indicated for other clinical sequelae (e.g., renal impairment, pulmonary infiltrates) Grade 4: Life-threatening; pressor or ventilatory support indicated Increase monitoring of vital signs as medically indicated until the subject is deemed medically stable in the opinion of the investigator. Hospitalization may be indicated. Subject is permanently discontinued from further trial treatment administration.	Crada 2:			
responsive to symptomatic medication and/or brief interruption of infusion); recurrence of symptoms following initial improvement; hospitalization indicated for other clinical sequelae (e.g., renal impairment, pulmonary infiltrates) Grade 4: Life-threatening; pressor or ventilatory support indicated Increase monitoring of vital signs as medically indicated until the subject is deemed medically stable in the opinion of the investigator. Hospitalization may be indicated. Subject is permanently discontinued from further trial treatment administration.				
medication and/or brief interruption of infusion); recurrence of symptoms following initial improvement; hospitalization indicated for other clinical sequelae (e.g., renal impairment, pulmonary infiltrates) Grade 4: Life-threatening; pressor or ventilatory support indicated Increase monitoring of vital signs as medically indicated until the subject is deemed medically stable in the opinion of the investigator. Hospitalization may be indicated. Subject is permanently discontinued from further trial treatment administration.				
of infusion); recurrence of symptoms following initial improvement; hospitalization indicated for other clinical sequelae (e.g., renal impairment, pulmonary infiltrates) Grade 4: Life-threatening; pressor or ventilatory support indicated Increase monitoring of vital signs as medically indicated until the subject is deemed medically stable in the opinion of the investigator. Hospitalization may be indicated. Subject is permanently discontinued from further trial treatment administration.				
symptoms following initial improvement; hospitalization indicated for other clinical sequelae (e.g., renal impairment, pulmonary infiltrates) Grade 4: Life-threatening; pressor or ventilatory support indicated Increase monitoring of vital signs as medically indicated until the subject is deemed medically stable in the opinion of the investigator. Hospitalization may be indicated. Subject is permanently discontinued from further trial treatment administration.	·			
improvement; hospitalization indicated for other clinical sequelae (e.g., renal impairment, pulmonary infiltrates) Grade 4: Life-threatening; pressor or ventilatory support indicated Increase monitoring of vital signs as medically indicated until the subject is deemed medically stable in the opinion of the investigator. Hospitalization may be indicated. Subject is permanently discontinued from further trial treatment administration.	,-	•		
indicated for other clinical sequelae (e.g., renal impairment, pulmonary infiltrates) Grade 4: Life-threatening; pressor or ventilatory support indicated Increase monitoring of vital signs as medically indicated until the subject is deemed medically stable in the opinion of the investigator. Hospitalization may be indicated. Subject is permanently discontinued from further trial treatment administration.	, .			
(e.g., renal impairment, pulmonary infiltrates) Corticosteroids Epinephrine Increase monitoring of vital signs as medically indicated until the subject is deemed medically stable in the opinion of the investigator. Hospitalization may be indicated. Subject is permanently discontinued from further trial treatment administration.	•	, ,		
